10.4. Correlative studies

Patients consented on this trial will have tumor samples analyzed for genomic alterations via next generation targeted sequencing. Optional post treatment biopsy will be obtained to compare the differences in genomic alterations prior to treatment and post treatment. In addition, circulating tumor DNA and circulating tumor RNA samples will be collected throughout treatment to serially assess the genomic profile of treated patients.

Gene sequencing will be performed in the CLIA certified Molecular Diagnostics Service laboratory, a division of the MSKCC Pathology Department, using IMPACT-Heme (Integrated Mutation Profiling for Actionable Cancer Targets Hematology Panel) with paired tumor and normal tissue samples, or a custom panel of genes depending on baseline IMPACT-Heme results. IMPACT provides full exon coverage of 410 cancer related genes including CARD11, MYD88, PIK3CA, BTK, and can be used to detect base substitutions, small indels, copy number alterations and select gene re-arrangements. In some cases, the Molecular Diagnostic Service will utilize an additional assay, such as Sanger Sequencing, B cell clonality, or fluorescence in situ hybridization (FISH), to confirm specific results from these multiplexed assays. We will assess for the following:

- 1) Determine variations on circulating tumor RNA throughout treatment
- 2) Correlate spectrum of genomic mutations in tumor tissue versus circulating tumor DNA
- 3) Assess tumor variant allele frequency in circulating tumor DNA
- 4) Correlate circulating tumor DNA to radiographic response

Table 10-1. Schedule of Evaluation

Timepoint	Screening	C1D1	C1D8	C1D15	CxD1	CxD8	CxD15	EOT	30 day FU after last dose ^H
Window	-28	-7		+/- 3 days	+/- 3 days	+/-3 days	+/-3 days	+/- 7 days	+/- 7 days
Treatment									
Copanlisib		X	X	X	X ^A	X ^A	X ^A		
Ibrutinib					Daily				
Evaluation									
Obtain Informed Consent	X								
Demography	X								
Inclusion/Exclusion criteria	X								
Medical/Diagnosis/Treatment history	X								
Prior/Concomitant medications	X		X	X	X				X ^K
Physical Examination	X		X	X	X			X	X
ECOG and Vitals (Weight, Blood pressure, Pulse, Resp, Temp)	X		X	X	X			X	
Hematology: CBC with Diff		X	X	X	X	X		X	
Chemistry(BMP, TBili, AST, ALT, TP, Alb, AP, UA, LDH, amylase, lipase, GFR, Mag, Phos)		X	X Fasting	X	X	X	X	X	
Lipid panel		X				Day 1 Cycle 3, 5, 7, 10, 13, 17, 21, 25, 29, 33			X
Urinalysis, Urine protein						As clinically indicated			X
T3, T4, TSH		X				As clinically indicated			X
Fructosamine		X			X	X			X
Hemoglobin A1c		X				X			X
Coagulation (PT/PTT)		X							X
B cell Clonality by NGS			X			Day 1 Cycle 3, 5, 7, 10, 13, 17, 21, 25, 29, 33			X
Hepatitis B/C ^B	X					Hepatotoxicity testing/procedures as clinically indicated ^C			
HIV	X								
Cytomegalovirus PCR	X					X			X
Serum/Urine beta-HCG for women of childbearing age		X							
Post Infusion Glucose Evaluation ^D			X ^D Fasting	X ^D	X ^D	X ^D	X ^D		
Post Infusion Blood Pressure ^E			X ^E	X ^E	X ^E	X ^E	X ^E		
Radiographic assessment ^F	X					Before Day 1 Cycle 3, 5, 7 (first 6 months), 10, 13, (1 year), 17, 21, 25, 31 (year 2-3)		X (if not within 4 weeks)	
ECHO or MUGA	X							X	
ECG	X							X	

PCP pneumonia prophylaxis			Continuous (unless clinically contraindicated)				
Pill Diary			X		X		X
Tumor biopsy(archived/fresh biopsy) ^G	X ^G				Optional ^G		
Research Blood Tests: ctDNA, ctRNA		X	X	X	Cycle 2: D1, D8, D15 Cycle 3-7: D1	X	
Research Blood Tests: Pharmacokinetics ^J				X			

A: Copanlisib Dosing: If copanlisib is held based on achievement of a complete response, patient visits will be every 2 cycles during C1-C6, every 3 cycles during C7-C12, every 4 cycles during C13-36.
B: Hepatitis Evaluation: HbsAg, HBcAb, anti-HCV Ab, Hep B/C PCR if positive
C: Additional viral hepatitis workup as clinically warranted: HAAb, HBsAg, HBsAb, HBcAb, HCV RNA or HDV RNA (where needed), H EAb, CMVAb, EBcAb, CMV IgM Ab, EBV IgM Ab, HSV, AP, CPK, LDH, Carriers of hepatitis B should be closely monitored for clinical and laboratory signs of active HBV infection, signs of hepatitis during and for several months following ibrutinib/copanlisib treatment. Carriers of hepatitis B (positive HBsAg and/or HBcAg but negative HBV-DNA is required to be on prophylactic antiviral therapy. If viral load becomes positive, patients should be withdrawn from study. Hep C carriers (anti-HCV Ab positive, negative HCV-RNA PCR must be tested monthly for HCV reactivation. If HCV-RNA PCR becomes positive, patients should be withdrawn from study.
D: Post Infusion Glucose Evaluation: C1D1 – fasting glucose prior to copanlisib (0h), 60 min (end of infusion) and 2 hours; all subsequent doses – non-fasting glucose prior to copanlisib (0h), post infusion.
E: Post Infusion Blood Pressure Evaluation: Blood pressure (5-10min, +/- 10 min) prior to copanlisib must be <150/90mmHg for two consecutive measurements. If blood pressure prior to infusion is ≥150/90 mmHg, medical intervention or dose delay should be considered. Blood pressure post infusion should be measured at 30 min (mid-infusion), 60 min (end of infusion), 1 hour and 2 hour post infusion (+/- 10 min).
F: Radiographic assessment via PET and CT chest/abdomen/pelvis and neck CT if clinically indicated (MRI will be used for those who are unable to undergo CT scans).
G: Pretreatment archived biopsy material (10-15 x 10 microns) or an optional pretreatment core biopsy (2-3 cores). Post treatment optional core biopsy (2-3 cores).
H: Maximum 36 cycles, not exceeding 36 months of treatment
J: Exact schedule for PK testing is in Table 9-4.
K: Not required to collect if patient has begun new anti-cancer therapy within 30 days after last dose of either study drug on protocol.

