- Patient has a concurrent active malignancy. Malignancies treated with a curative intent with an expected life expectancy \geq 5 years or a non-competing life expectancy risk are eligible (i.e. adequately treated basal or squamous cell carcinoma, non-melanomatous skin cancer, early stage breast cancer, treated prostate cancer or any other cancer from which the patient has been disease free for \geq 3 years).
- Patient with known history of human immunodeficiency virus (HIV), or any uncontrolled active systemic infection.
- Patient has CMV viremia (peripheral blood CMV PCR positive), acute viral hepatitis (typically defined by elevated AST/ALT), or a history of chronic or active HBV or HCV infection. HBV infection is defined as having HBsAg and/or HBcAb positive test with concurrent detectable HBV DNA levels. HCV infection is defined as detectable HCV RNA levels.
- Patient requires treatment with a strong or moderate cytochrome P450 (CYP) 3A4 inhibitors, and inducers, and the treatment cannot be discontinued or switched to a different medication prior to starting study drug. Moderate and strong CYP modulators (inducers and inhibitors) should have a washout period of at least 5-6 half-lives before initiating ibrutinib or copanlisib.
- Patients with known bleeding diathesis (e.g. von Willebrand 's disease) or hemophilia
- Patient is currently receiving warfarin or other Vitamin K antagonist. Therapy with heparin, low molecular weight heparin (LMWH), or fondaparinux is allowed. Refer to Section 9.5 for Concomitant medication
- Patients with Child Pugh Class B or C hepatic cirrhosis
- Patients with any life threatening illness, medical condition or organ system dysfunction that in the opinion of the investigator could compromise the subject's safety, interfere with absorption of metabolism of study drugs or put the study outcomes at undue risk.

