8.1 PRETREATMENT EVALUATION

Prior to initiating treatment:

- Prior biopsy with pathologic confirmation of MCL.
- Archival block 10-15 x 10 micron unstained slides and 1 H&E will be requested. A minimum of 40 micron material is requested.
- If archival tissue is not available, patients will be asked to provide informed consent for an optional repeat biopsy.

Within 4 weeks prior to initiating treatment:

- Medical history and demographics
- Complete history and physical exam (including weight, pulse, blood pressure, temperature, ECOG performance status)
- Medication review
- Hepatitis B surface antigen and Hepatitis B core antibody (HBV DNA PCR is only required if HBsAg is positive)
- Hepatitis C antibody
- HIV testing
- Cytomegalovirus PCR testing
- ECG
- Echocardiogram or MUGA to evaluate cardiac function
- PET scan
- CT chest/abdomen/pelvis and neck CT if clinically indicated (MRI will be used for those who are unable to undergo CT scans).

Within 1 week prior to initiating treatment:

- Blood work: CBC with differential, PT/INR, electrolytes (Na, K, Cl, CO2), BUN, Cr, total bilirubin, total protein, albumin, AST, ALT, alkaline phosphatase, uric acid, LDH, magnesium, phosphorus, lipid panel, thyroid function tests, hemoglobin A1c, fructosamine, amylase, lipase, urinalysis, GFR
- Serum beta-HCG (for WOCBP only) to assess for pregnancy

[figure not shown]

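### Table 10-1 footnote C ties mandatory hepatitis B prophylaxis to HBcAg, very probably a slip for HBcAb, and its viral-load withdrawal rule has no scheduled on-treatment HBV DNA test

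*Combined protocol and SAP*

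**What the plan says.** Section 6.3 excludes patients with hepatitis B infection and defines the term: "HBV infection is defined as having HBsAg and/or HBcAb positive test with concurrent detectable HBV DNA levels". A patient with a positive marker but undetectable DNA is therefore not excluded by that definition. Section 8.1 lists the screening markers as "Hepatitis B surface antigen and Hepatitis B core antibody".

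In Table 10-1 (Section 10.4), the Hepatitis B/C row has a mark at screening. Its on-treatment cell reads "Hepatotoxicity testing/procedures as clinically indicated". Footnote B, attached to that row, reads "Hepatitis Evaluation: HbsAg, HBcAb, anti-HCV Ab, Hep B/C PCR if positive".

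Footnote C then does four things for hepatitis B:

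- It lists further tests: "Additional viral hepatitis workup as clinically warranted: HAAb, HBsAg, HBsAb, HBcAb, HCV RNA or HDV RNA (where needed", followed by other items.
- It asks for general vigilance: "Carriers of hepatitis B should be closely monitored for clinical and laboratory signs of active HBV infection".
- It makes prophylaxis mandatory: "Carriers of hepatitis B (positive HBsAg and/or HBcAg but negative HBV-DNA is required to be on prophylactic antiviral therapy".
- It sets a withdrawal rule: "If viral load becomes positive, patients should be withdrawn from study".

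For HCV carriers the same footnote requires a monthly test for reactivation. Section 9.8 requires CMV PCR every cycle.

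**The concern.** Both rules in footnote C are operative safety rules, and each lacks something it needs to work as written.

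The prophylaxis rule names a marker that nobody is asked to measure. If site staff follow the words, the core-marker part of the rule can never be triggered, and a carrier identified only by HBcAb is not required to receive antiviral cover. The infectious-prophylaxis guidance in Section 9.8 deals with CMV and Pneumocystis only, so no other text fills the gap.

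The withdrawal rule acts on a viral load that no visit is scheduled to measure. When a patient is withdrawn then depends on when someone chooses to order the test. This matters most while copanlisib is held for complete response: ibrutinib continues, and Section 10.2 spaces visits widely.

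**Working it through.** The check is mainly a comparison of texts. There is no stated figure to reproduce.

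**Step 1: which core marker does the protocol use?**

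| Place | Core marker |
|---|---|
| Section 6.3, definition of HBV infection | HBcAb |
| Section 8.1, screening tests | core antibody |
| Table 10-1 footnote B | HBcAb |
| Table 10-1 footnote C, workup list | HBcAb |
| Table 10-1 footnote C, prophylaxis rule | HBcAg |

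Four of the five places use the antibody. The exception is the one that triggers treatment. Section 6.3 uses the same HBsAg and/or construction with HBcAb, which supports reading HBcAg as a slip.

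**Step 2: who is covered by the prophylaxis rule?** All patients below are HBV DNA-negative, so Section 6.3's definition does not exclude them.

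| HBsAg | HBcAb | Prophylaxis required, literal text | Prophylaxis required, if HBcAb is meant |
|---|---|---|---|
| + | + | yes | yes |
| + | − | yes | yes |
| − | + | no | yes |

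Only the last row changes. Section 8.1 and footnote B also differ on when baseline HBV DNA must be measured. That is a separate matter, and nothing here depends on it.

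**Step 3: which on-treatment viral tests have a stated interval?**

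| Virus | Stated interval | Source |
|---|---|---|
| CMV | every cycle (up to 36) | Section 9.8; maximum treatment in Section 4.3 |
| HCV, in carriers | monthly | footnote C |
| HBV, in carriers | none | Hepatitis B/C row, footnotes B and C |

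Scheduled on-treatment HBV DNA tests: 0.

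**Step 4: how far apart are visits while copanlisib is held?** Section 10.2 gives visits every 3 cycles in C7-C12 and every 4 cycles in C13-C36, with 28-day cycles.

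- C7-C12: 3 × 28 = 84 days between visits; 6 / 3 = 2 visits.
- C13-C36: 4 × 28 = 112 days between visits; 24 / 4 = 6 visits.
- Total if held from cycle 7 to cycle 36: 2 + 6 = 8 visits in 30 cycles.

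Safeguards tied to scheduled visits, including routine AST and ALT, are therefore thinnest in this period.

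**The case against.** The strongest reply is that the first part is a one-letter error any hepatology-aware reader would correct, and that the second understates existing cover. Much of this stands.

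- The marker is an evident slip. A reader might infer that the protocol means to leave HBcAb-only carriers without prophylaxis. The documents do not support that: every other statement points to HBcAb. What remains is that a mandatory treatment rule should not need correcting by its reader.
- A reader might infer that HBV DNA cannot be ordered on treatment because footnote C's list omits it. That is wrong. The list is headed as additional workup, and footnote B on the same row already provides for PCR when a marker is positive.
- A reader might infer that reactivation would go unnoticed. That is also unsupported. Footnote C asks for close monitoring, AST and ALT are in the scheduled chemistry panel, Table 9-7's notes require at least weekly liver tests after a grade 2 or higher rise, and Section 13 lists active HBV infection as a ground for removal. However, none of these sets an interval for viral load, which is the trigger the withdrawal rule uses.
- The monthly HCV rule is an imperfect comparator. Footnote C mandates antiviral prophylaxis for HBV carriers and states none for HCV carriers, so different monitoring could be deliberate. The contrast shows that the footnote can state an interval; it does not show that monthly is right for HBV.
- Section 6.3 also mentions a history of chronic or active HBV, which could suggest that carriers cannot enrol. Its definition requires detectable DNA, however, and footnote C provides for DNA-negative carriers, so the protocol plainly expects some.

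**Conclusion.** The concern holds, with limits. Footnote C's prophylaxis rule names a marker the protocol does not test and, taken literally, omits one eligible group: HBsAg-negative, HBcAb-positive, DNA-negative patients. Its HBV withdrawal rule has zero scheduled on-treatment viral-load tests behind it, with only partial cover from other provisions.

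That HBcAg stands for HBcAb is an inference, though a well-supported one. The number of patients affected is unknown and could be zero: Section 14.2 gives a maximum of 45 treated patients, but the documents state neither carrier prevalence nor reactivation rate, so no estimate of harm is offered. The point concerns patient safety only and does not touch the sample size, the error rates or the primary analysis. The correction is worth making because the rules are mandatory and the change is small.

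**What to change.** 1. In footnote C, change HBcAg to HBcAb in the prophylaxis rule.
2. Add a row to Table 10-1 for HBV DNA PCR in carriers only (HBsAg- or HBcAb-positive), drawn with the CMV PCR that Section 9.8 already requires every cycle. While copanlisib is held for complete response, draw it at each scheduled visit.

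The cost is one corrected marker, one table row and one extra assay on existing blood draws for any carriers enrolled. A carrier on combination therapy throughout would have up to 36 tests. A carrier whose copanlisib is held from cycle 7 to cycle 36 would have up to 6 + 8 = 14. The remaining limitation is that, during a hold, the gap between tests is still 84 to 112 days; the existing liver-test and close-monitoring provisions have to cover it.

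Nothing further is needed for this point. Footnote B already makes the PCR available, so footnote C's workup list can stay as it is. Lab-only draws between visits, or a monthly programme after treatment ends, would exceed what a rule for withdrawing patients requires.

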11.0 TOXICITIES/SIDE EFFECTS

11.1. Adverse Event

11.1.1. Definitions and reporting

An adverse event is defined as the appearance of (or worsening of any pre-existing) undesirable sign(s), symptom(s), or medical condition(s) that occur after patient's signed informed consent has been obtained. Abnormal laboratory values or test results occurring after informed consent constitute adverse events only if they induce clinical signs or symptoms, are considered clinically significant, require therapy (e.g. hematologic abnormality that requires transfusion or hematological stem cell support), or require changes in study medication(s).

Adverse events that begin or worsen after informed consent should be recorded in Medidata. Conditions that were already present at the time of informed consent should be recorded in the Medical History in Medidata. Adverse event monitoring should be continued for at least 30 days following the last dose of study treatment or until initiation of new therapy, whichever comes first. Adverse events (including lab abnormalities that constitute AEs) should be described using a diagnosis whenever possible, rather than individual underlying signs and symptoms. When a clear diagnosis cannot be identified, each sign or symptom should be reported as a separate Adverse Event.

Adverse events will be assessed according to the Common Terminology Criteria for Adverse Events (CTCAE) version 5.0. If CTCAE grading does not exist for an adverse event, the severity of mild, moderate, severe, and life-threatening, corresponding to Grades 1 - 4, will be used. CTCAE Grade 5 (death) will not be used in this study; rather, information about deaths will be collected through a Death form.

The occurrence of adverse events should be sought by non-directive questioning of the patient (subject) during the screening process after signing informed consent and at each visit during the study. Adverse events also may be detected when they are volunteered by the patient (subject) during the screening process or between visits, or through physical examination, laboratory test, or other assessments. As far as possible, each adverse event should be evaluated to determine:

- The severity grade (CTCAE Grade 1-4)
- Its duration (Start and end dates)
- Its relationship to the study treatment (Reasonable possibility that AE is related: No, Yes) or its relationship to the study treatment (Reasonable possibility that AE is related: No, Yes, investigational treatment, Yes, the study treatment (non-investigational), Yes, both and/or indistinguishable)
- Action taken with respect to study or investigational treatment (none, dose adjusted, temporarily interrupted, permanently discontinued, unknown, not applicable)
- Whether medication or therapy taken (no concomitant medication/non-drug therapy, concomitant medication/non-drug therapy)
- Outcome (not recovered/not resolved, recovered/resolved, recovering/resolving, recovered/resolved with sequelae, fatal, unknown)
- Whether it is serious, where a serious adverse event (SAE) is defined as in Section 11.2.1

- All adverse events should be treated appropriately. If a concomitant medication or non-drug therapy is given, this action should be recorded in Medidata.
- Once an adverse event is detected, it should be followed until its resolution or until it is judged to be permanent, and assessment should be made at each visit (or more frequently, if necessary) of any changes in severity, the suspected relationship to the study treatment, the interventions required to treat it, and the outcome.
- Progression of malignancy (including fatal outcomes), if documented by use of appropriate method (Cheson criteria), should not be reported as a serious adverse event.
- Adverse events separate from the progression of malignancy (example, deep vein thrombosis at the time of progression or hemoptysis concurrent with finding of disease progression) will be reported as per usual guidelines used for such events with proper attribution regarding relatedness to the drug.

11.1.2. Laboratory test abnormalities

Laboratory abnormalities that constitute an Adverse event in their own right (are considered clinically significant, induce clinical signs or symptoms, require concomitant therapy or require changes in study treatment), should be recorded in Medidata. Whenever possible, a diagnosis, rather than a symptom should be provided (e.g. anemia instead of low hemoglobin). Laboratory abnormalities that meet the criteria for Adverse Events should be followed until they have returned to normal or an adequate explanation of the abnormality is found. When an abnormal laboratory or test result corresponds to a sign/symptom of an already reported adverse event, it is not necessary to separately record the lab/test result as an additional event.

Laboratory abnormalities, that do not meet the definition of an adverse event, should not be reported as adverse events. A Grade 3 or 4 event (severe) as per CTCAE does not automatically indicate a SAE unless it meets the definition of serious as defined below and/or as per investigator's discretion. A dose hold or medication for the lab abnormality may be required by the protocol in which case the lab abnormality would still, by definition, be an adverse event and must be reported as such.

11.2. Serious Adverse Event

A serious adverse event is one that is fatal or life-threatening (see below), is temporarily or permanently disabling, requires inpatient hospitalization (initial or prolonged), or is associated with a congenital anomaly, a new cancer or a drug overdose (either accidental or intentional). In addition, any event suggesting a significant hazard, contraindication, side effect or precaution should also be considered serious.

11.3. Life-threatening event

The event is an immediate risk of death from the reaction as it occurred. Life-threatening does not include a reaction that, had it occurred in a more serious form, might have caused death. For example, drug-induced hepatitis that resolved without evidence of hepatic failure would not be considered life-threatening even though drug-induced hepatitis can be fatal.

11.4. Reporting procedures for adverse events

All adverse events occurring during the study, observed by the investigator or reported by the subject, will be reported to the IRB either in memorandum form or on the Medidatotoxicity form. The following attributes must be assigned: description; dates of onset and resolution; severity; assessment of relatedness to study drug, other suspect drug, or device; and action taken. The investigator may be asked to provide follow-up information.

11.5. Ibrutinib anticipated toxicities

Ibrutinib is an FDA approved drug for mantle cell lymphoma.

Likely (>20%): Diarrhea, nausea, constipation, abdominal pain, vomiting, upper respiratory tract infection, fatigue, peripheral edema, bruising, rash, musculoskeletal pain, dyspnea, decreased appetite, platelets decreased, neutrophils decreased, hemoglobin decreased

Less Likely (4-20%): stomatitis, dyspepsia, urinary tract infection, pneumonia, skin infections, sinusitis, pyrexia, asthenia, petechiae, muscle spasms, arthralgia, cough, epistaxis, dehydration, dizziness, headache, hyperuricemia, hemorrhage (gastrointestinal bleeding, hematuria and post procedural hemorrhage), hypertension, second primary malignancies- most common non-melanoma skin cancer

Rarely (<3%): intracranial and subdural hematoma, cardiac arrhythmias, lymphocytosis, tumor lysis syndrome, progressive multifocal leukoencephalopathy

Most side effects listed above have been mild to moderate in severity; however severe side effects have occurred. Some side effects have been severe enough to lead to study drug discontinuation, dose modification or reduction, hospitalization, disability and sometimes death.

